Appendix B. Code Fragments

The ORR and its 95% CI can be calculated in SAS using PROC FREQ. The sample code is provided below, where RESP is the status of response (eg., 1=responder, 2=non-responder). The CI using the exact method can be found in the OUT data labeled as 'Exact Conf Limits'.

```
proc freq data=TEST;  
  tables RESP / binomial alpha=0.05;  
  ods output Binomial=OUT;  
run;
```

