3.3 Adaptive Design

Part 1

A two-parameter Bayesian Logistic Regression Model (BLRM) is used to guide dose escalation. The maximum tolerated dose (MTD) target Toxicity Probability Interval (TPI) for dose-limiting toxicity (DLT) is (0.20, 0.33] and TPIs of (0.33, 0.60] and (0.60, 1.00] are defined as excessive and unacceptable, respectively. The design seeks to identify a dose most likely to have a DLT rate in the target TPI, but with overdose control that limits

the possibility the dose has an excessive or unacceptable DLT rate (Babb et al, 1998). The overdose control limit is defined as less than a 0.40 probability of an excessive or unacceptable TPI. Based on accumulating safety data, the DLRT may implement an overdose control limit of less than a 0.25 probability of an excessive or unacceptable TPI. The probability of a DLT at dose level d_i is assumed to follow a Bernoulli distribution with probability π_i where the logit of π_i increases linearly with the log of the standardized dose in the following 2-parameter logistic model:

$$\log [\pi_i / (1-\pi_i)] = \text{logit}(\pi_i) = \log[a] + \exp(\log[b]) \log (d_i / d_{ref})$$

Where a and b are random variables and d_{ref} is one of the planned doses selected as the reference dose.

A bi-variate normal prior distribution (Neuenschwander et al, 2008) is used for $\theta = (\log a, \log b)$ where the probability that the true DLT rate is ≤ 0.40 at the lowest planned dose of 80 mg is 0.90 and the probability the true DLT rate is ≤ 0.05 at the reference dose of 640 mg is 0.05. These values are selected such that π_i is 0.05 for the starting dose and 0.25 for the reference dose. Model sensitivity to the prior will also be investigated and in particular the BLRM will be examined using a prior having a lower reference dose (eg, 320 mg).

Part 2 and Part 3

Each dose cohort will initially enroll 2-4 subjects in Parts 2A and 2C and 3-4 subjects in Part 3; and up to 10 subjects at the highest dose level or MTD/MTCD may be enrolled. After reviewing all available safety and tolerability data, dose level decisions will be made by the DLRT using a mTPI model based on all evaluable subjects that have been enrolled at current dose. Dose escalation is considered to be complete if one of the following rules is met:

- **The highest planned dose level is evaluated, MTCD has not been defined and no DLTs occur at any dose level.**
- **An MTD or MTCD is identified.**

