- **IMWG-URC for MM**
- **2017 ELN criteria for AML**
- **Revised IWG for MDS**
- **Lugano Classification for NHL**

Dose Limiting Toxicity (DLT)

Unless otherwise specified, investigators determine whether an adverse event qualifies as a DLT per the definition described in the protocol.

DLT Observation Period

The DLT observation period is defined as, at minimum, 28 days after the initial dose of AMG 397. If lead-in dosing period is initiated, the DLT-observation period is defined as the amount of time for subject(s) for each dose cohort to receive at least 1 week of lead-in dose and 3 weeks of target dose.

Duration of Response (DOR)

Duration of response is calculated for subjects who have achieved response (PR or better). It is defined as time from the first observation indicating a response to the subsequent date of disease progression or death, whichever is earlier.

DOR time in months: (date of disease progression or death - date of the first observation of response +1)/30.4

Subjects without disease progression or death until the analysis data cut-off date will be censored at the last adequate disease assessment date.

Fridericia-corrected QT Interval (QTcF)

The Fridericia correction will be calculated from the investigator reported QT (msec) and RR interval (msec): $QTcF = QT / (RR/1000)^{1/3}$

Investigational Product (IP)

IP is used in reference to AMG 397.

Overall Response Rate (ORR)

ORR is the incidence of either PR or better based on investigator assessment. All subjects that do not meet the criteria for response (PR or better) by the analysis cutoff date will be considered as non-responders.

Progression-free survival (PFS)

PFS time is calculated as time from first dose of IP date to disease progression date or death due to any cause, whichever is earlier.

PFS time in months: (date of disease progression or death - first dose of IP date +1)/30.4

Subjects without disease progression or death until the analysis data cut-off date will be censored at the last adequate disease assessment date. If no post-baseline disease assessment, censoring is at the first dose of IP date.

Overall survival (OS)

OS is defined as the time from first dose of IP date until death due to any cause.

OS time in months: (date of death - first dose of IP date +1)/30.4

Patients without event will be censored at their last date known to be alive.

Study Day

Post study day 1: study day = (date –Study Day 1) + 1

Pre study day 1: study day = (date –Study Day 1)

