9.1 General Considerations

Descriptive statistics on continuous data will include means, medians, standard deviations and ranges, while categorical data will be summarized using frequency counts and percentages. Graphical summaries of the data may also be presented. When data are summarized by time, the values recorded against the scheduled time points listed in the protocol will be used. When assessing minimum/maximum increases or decreases over the study, all assessments, including unscheduled assessments will be used.

For each indication, efficacy and safety data will be summarized by dose level.

For the subjects who complete the DLT period and proceed to a higher dose level or crossover to a combinational therapy cohort for the following treatment cycle,

efficacy and safety data will be summarized per their initial assigned dose level.

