9.5 Efficacy Analyses

Table 2. Efficacy Endpoints

Endpoint	Statistical Analysis Methods
Overall response rate	The proportion of subjects with response to treatment with corresponding 2-sided exact 95% CI will be calculated using the Clopper-Pearson method (Clopper and Pearson, 1934) for the Full Analysis Set. Refer Appendix B for code fragment.
DOR, PFS, and OS	Kaplan-Meier estimates and Kaplan-Meier curve will be provided for the Full Analysis Set.
TTR	Descriptive statistics will be provided for subjects with response.
MRD[-] status at CR (Parts 3B and 3C only)	Proportion of MRD[-] at CR will be provided for subjects with CR.

For time to event endpoints (including DOR, TTR, OS, and PFS), summary table or figure may not be generated if the number of events is less than 10. The individual subject-level data will be provided.

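### The SAP's sample code for ORR fixes no response level and keeps no zero count, so a cell with no responders would return the non-responder proportion (100%)

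*SAP*

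**What the plan says.** SAP Section 9.5, Table 2, sets the ORR analysis: "The proportion of subjects with response to treatment with corresponding 2-sided exact 95% CI will be calculated using the Clopper-Pearson method". The same cell then says "Refer Appendix B for code fragment".

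Appendix B describes the input as follows: "RESP is the status of response (eg., 1=responder, 2=non-responder". The procedure call is "tables RESP / binomial alpha=0.05", with the binomial output saved to a dataset named OUT. On where to find the interval, it says: "The CI using the exact method can be found in the OUT data labeled as 'Exact Conf Limits". The fragment has no LEVEL= option, no WEIGHT statement with zero counts, and no rule for a group without responders.

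The definition of ORR in SAP Section 5 keeps everyone in the denominator: "All subjects that do not meet the criteria for response (PR or better) by the analysis cutoff date will be considered as non-responders".

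The reporting cells are small. Section 9.1 says "For each indication, efficacy and safety data will be summarized by dose level", and Section 3.3 says "Each dose cohort will initially enroll 2-4 subjects in Parts 2A and 2C and 3-4 subjects in Part 3", with up to 10 at the highest dose level or at the MTD/MTCD.

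**The concern.** The binomial proportion from PROC FREQ refers to one level of the variable. When the code does not name that level, the default is the first one present in the data. With the coding in Appendix B this is the responder level only if at least one subject responded. If nobody responded, level 2 is the only level, and OUT then holds the proportion of non-responders with its exact limits.

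The error reverses the result in the drug's favour. Nothing else in the SAP covers this case. The Section 9.5 allowance to omit summaries with fewer than 10 events applies only to time-to-event endpoints, so ORR is still reported in very small cells. Section 7.1 allows efficacy to be examined after each cohort, when cells are smallest.

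**Working it through.** **Inputs.** Coding and code: SAP Appendix B. Method (Clopper-Pearson, two-sided 95%): Section 9.5, Table 2. Cell sizes: Section 3.3 (2 to 4, up to 10) and Section 3.2 (20 per expansion group). Illustrative ORR of 20%: Section 3.2. The rates of 10% and 30% are assumptions, added to show a range. The first-level default is an assumption about the software, emulated in Python.

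**The plan's own figure.** For 4 responders in 20, the Clopper-Pearson limits are 5.73% and 43.66%. These round to the 6% to 44% in Section 3.2, so the stated method reproduces.

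**The fragment with at least one responder.** Level 1 is the first level present. The fragment gives 20% (5.7% to 43.7%) for 4/20 and 25% (0.6% to 80.6%) for 1/4. Both are right.

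**The fragment with no responders.** Level 2 is the only level, so the code evaluates n/n instead of 0/n.

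- Correct upper limit for 0/n: 1 − 0.025^(1/n). For n=4: 1 − 0.3976 = 0.602.
- Lower limit that the code gives for n/n: 0.025^(1/n). For n=4: 0.398.
- Chance of no responders: (1 − ORR)^n. For n=4 at 20%: 0.8^4 = 0.4096.

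| n | Correct result for 0/n | Fragment returns | P(no responders), ORR 20% | ORR 10% (assumed) | ORR 30% (assumed) |
|---|---|---|---|---|---|
| 2 | 0% (0 to 84.2%) | 100% (15.8 to 100%) | 64% | 81% | 49% |
| 3 | 0% (0 to 70.8%) | 100% (29.2 to 100%) | 51% | 73% | 34% |
| 4 | 0% (0 to 60.2%) | 100% (39.8 to 100%) | 41% | 66% | 24% |
| 6 | 0% (0 to 45.9%) | 100% (54.1 to 100%) | 26% | 53% | 12% |
| 10 | 0% (0 to 30.8%) | 100% (69.2 to 100%) | 11% | 35% | 2.8% |
| 20 | 0% (0 to 16.8%) | 100% (83.2 to 100%) | 1.2% | 12% | 0.1% |

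For n=4, the estimate and limits from a cell with no responders are identical to those from a true 4/4 response.

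**The case against.** The best defence is that Appendix B is only an illustration. It calls itself sample code, introduces the coding as an example, uses a placeholder dataset and has no step that splits by indication or dose level. The governing text, in Section 9.5 and the ORR definition in Section 5, is correct, and a program that returned 100% for 0/n would breach it. Section 8.7 provides for validated standard macros where they can produce the output, and for verification of output. It is therefore not shown that this fragment would be the production code. All of this stands, and it limits the severity. It does not make the fragment right: Table 2 points to it, it is the only ORR code in the SAP, and Section 8.7 names no zero-responder check. A second programmer working from Appendix B would get the same number.

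Three stronger readings are tempting, and the documents do not support them.

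- A reader might infer that the SAP tells the programmer to take the ORR itself from OUT. Appendix B points to OUT only for the confidence interval. If the responder count came from elsewhere, the result would be 0% beside limits of 39.8% to 100% for n=4. That is still wrong, but conspicuous.
- A reader might infer that zero responders is the normal outcome in these cells. At 20% it is more likely than not only for n=2 and n=3, and in the expansion groups of 20 it is rare.
- A reader might infer that the main conclusions of the trial are at risk. ORR is a secondary, descriptive endpoint. Section 2.2 plans no formal hypothesis test, dose decisions rest on safety data and the mTPI guidelines, and no rule in the SAP depends on the ORR interval.

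**Conclusion.** The point holds as a defect in the Appendix B sample code. Run as written on a cell with no responders, the fragment gives the non-responder proportion and its limits: 100% (39.8% to 100%) for 0/4 and 100% (69.2% to 100%) for 0/10. It is correct in every cell with at least one responder. The ORR definition, the choice of Clopper-Pearson and the precision example for 20 subjects need no change.

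The conclusion rests on two assumptions: that PROC FREQ uses the first level present when none is named, and that a programmer follows the fragment and its example coding. The first should be confirmed with one run in SAS. Severity is should-fix: the error is silent in the saved dataset and the trigger is common in cohorts of 2 to 4, but a sound written specification and general verification stand between the fragment and a report.

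**What to change.** Replace the fragment in Appendix B with one that does the following.

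1. For each indication-by-dose cell, first summarize to a count dataset that always holds two rows, RESP=1 and RESP=2, with zero counts kept.
2. Add `weight COUNT / zeros;`.
3. Use `tables RESP / binomial(level='1') alpha=0.05;`.

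Naming the level alone is not enough, because level 1 is absent from subject-level data when nobody responds.

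State in Appendix B that both the estimate and the limits are for the responder level. Add a programming check that 0/n returns 0% with upper limit 1−0.025**(1/n), for example 60.2% for n=4 and 30.8% for n=10. Check any ORR output already produced with this fragment for cells with no responders.

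The cost is a small pre-summary step, a few lines of code and one test case. No data collection, endpoint or statistical method changes.

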Appendix C. Reference Values/Toxicity Grades

Adverse Event Grading Scale

The CTCAE is available at the following location:

https://ctep.cancer.gov/protocoldevelopment/electronic_applications/ctc.htm
